9.7.1.6 Efficacy Analyses

ADAPTIVE TRIAL DEFINITIONS

Clinically Significant Difference (CSD): The CSD used in the adaptive model relative to the change from baseline over time for placebo in the ADCOMS. The CSD for this study represents an approximate 25% reduction compared to placebo in the progression of AD as measured by the ADCOMS.

Maximum Effective Dose (d_{Max}): The dose that achieves the greatest treatment effect

ED₉₀: The ‘simplest’ dose regimen that achieves at least 90% of the d_{Max} treatment effect. The term ‘simplest’ reflects the preference for dosing frequency and amount when considering the treatment arms for the study and while taking efficacy into account (monthly administration is preferred over biweekly administration and lower doses are preferred over higher doses, with priority placed on frequency of administration). Thus, the rank order of prioritized doses (beginning with the simplest) is: 5 mg/kg Q4wk, 10 mg/kg Q4wk, 2.5 mg/kg Q2wk, 5 mg/kg Q2wk, and 10 mg/kg Q2wk.

Early Success: The study meets early success criteria if the probability that the ED₉₀ is better than the placebo by the CSD is at least 0.95. Early success is achieved before all subjects complete 12 months of treatment and can only be determined once ≥ 350 subjects are randomized. If early success is declared prior to full enrollment, randomization of new subjects will stop, outside Japan. Sites in Japan will randomize up to 40 Japanese subjects even if early success is declared or the study achieves 800 subjects randomized. All randomized Japanese subjects in the study will receive up to 18 months of treatment in the Core Study and are eligible to participate in the Extension Phase if implemented. (revised per Amendments 07, 08, and 11)

Futility: The study meets statistical futility criteria if the probability that the ED₉₀ is better than the placebo by the CSD is less than 0.05 (with ≤ 300 subjects randomized) or 0.075 (with ≥ 350 subjects randomized) at 12 months of treatment. If the study meets statistical futility criteria, the sponsor will make the final decision pertaining to study futility after reviewing recommendations by the DSMB. Based on the sponsor's final decision, if the study continues after statistical futility criteria are met, it will be considered a failed study. (revised per Amendment 01)

The study will be considered a success if either of the following criteria are met:

1. The study meets early success criteria
2. The study reaches complete randomization and the Bayesian analysis at completion of 12 months of treatment results in an ED₉₀ with at least an 80% probability of being better than the placebo by the CSD (revised per Amendment 09)

ANALYSIS OF PRIMARY EFFICACY ENDPOINT (REVISED PER AMENDMENT 09)

The primary analysis will be based on subjects from the Full Analysis Set with the prespecified censoring rules applied. Japanese subjects who are randomized after early success is declared or the study achieves 800 subjects randomized will not be included in the primary analysis. (revised per Amendment 07) The primary endpoint is the change from baseline to 12 months in the ADCOMS. The ADCOMS is a weighted linear combination of 12 items from the 3 existing clinical scales, the ADAS-Cog, the MMSE, and the CDR. These 12 items consist of the predictive variables A4, A7, A8, A11, M1, M7, C1, C2, C3, C4, C5, and C6, which have been selected from the clinical scales, the ADAS-Cog, the MMSE, and the CDR. The names of these item and the corresponding scale names are described in [Table 10](#).

Table 10 Predictive Variables for the ADCOMS

Scale	Item ID	Item Name	PLS weight
ADAS-Cog	A4	Delayed Word Recall	0.00847483
	A7	Orientation	0.017088
	A8	Word Recognition	0.003732761
	A11	Word Finding	0.016211
MMSE	M1	Orientation Time	0.041567
	M7	Drawing	0.038238
CDR	C1	Personal Care	0.054321
	C2	Community Affairs	0.1091
	C3	Home and Hobbies	0.089039
	C4	Judgment and Problem Solving	0.069493
	C5	Memory	0.058724
	C6	Orientation	0.078152

ADAS-Cog = Alzheimer’s Disease Assessment Scale, cognitive subscale, CDR = Clinical Dementia Rating, ID = identification, MMSE = Mini-Mental State Examination, PLS = Partial Least Squares.

The maximum ADCOMS is achieved when each item is assigned the maximum score. This maximum composite score is 1.97. The range of this new composite score is therefore between 0 and 1.97.

The primary endpoint is the change from baseline to 12 months in the ADCOMS. The dose response of the primary endpoint is modeled with a 2-dimensional first-order normal dynamic linear model, where Normal and Inverse-Gamma priors are used. The primary efficacy analysis will calculate the Bayesian posterior probability that the dose identified is the most likely ED₉₀ dose that achieves the CSD compared to the placebo arm. At each Bayesian analysis, 3 Bayesian probabilities will be summarized for each active dose: the probability of being the ED₉₀ dose, the probability of being statistically superior to placebo, and the probability of being statistically superior to placebo by the CSD. The study will be considered a success in the Bayesian analysis at the completion of 12 months of treatment if there is at least an 80% probability that the ED₉₀ achieves the CSD from placebo. (revised per Amendment 09)

For the clinical efficacy data (ie, derived Clinical Composite Score, MMSE, CDR-SB, ADAS-Cog, and FAQ), subjects will be censored at the time of initiation of new AChEIs or memantine treatment regimens if they were not on AChEIs or memantine at randomization, and will be censored at the time of dose adjustment of AChEIs or memantine if they were already on stable treatment with AChEIs or memantine at randomization. The value of the primary endpoint for censored subjects will be imputed using data up to the censoring time and the Bayesian imputation method.

After unblinding, the primary endpoint will be analyzed using the Bayesian methods described above as well as conventional statistical methods. The following additional Bayesian analyses will be conducted as sensitivity analyses: (revised per Amendment 01)

- The primary endpoint will be analyzed regardless of initiation of new AChEIs or memantine or dose adjustment of stable AChEIs or memantine, using the same Bayesian analysis method as in the primary analysis. (revised per Amendment 01)
- In case of early success, the primary analysis as well as the above sensitivity analyses will be repeated after all subjects have either completed 12 months follow up or are lost to follow-up. (revised per Amendment 01)

Statistical methods for the conventional analyses of primary efficacy endpoint will use a mixed effects model with repeated measures (MMRM) comparing placebo to the identified ED₉₀ dose from the Bayesian analysis (revised per Amendment 09). The model will include randomization of stratification variables, clinical subgroup (MCI due to AD, mild AD), the presence or absence of ongoing AD treatment (ie, AChEIs or memantine or both), *APOE4* status (positive, negative), and baseline Composite Clinical Score as covariates. These analyses will be performed on the Full Analysis Set as well as the PP set based on the ITT principle. In case of early success, the conventional analyses will also be performed using the data collected prior to the IA. (revised per Amendment 01)

ANALYSIS OF KEY SECONDARY EFFICACY ENDPOINTS (REVISED PER AMENDMENTS 09 AND 10)

Key Secondary endpoints were ordered to reflect the most recent FDA Draft Guidance and EMA Guideline that prioritizes effects on pathophysiology in early AD, as measured by biomarkers (February, 2018). Conventional analysis will be performed using all available data at the time of success (if applicable), and at 18 months of treatment, regardless of success. An MMRM will be used to compare the combined 10 mg dose group (including biweekly and monthly regimens) with placebo for the key secondary endpoints (revised per Amendments 09 and 10). The rationale for combining the two 10-mg dose regimens is to account for the loss of subjects positive for *APOE4* in the 10 mg/kg biweekly dose group and the inability to randomize *APOE4* carriers to the 10 mg/kg biweekly group following a Regulatory request by European Health Authorities in July, 2014. The key Secondary endpoint based on clinical status (ADCOMS, CDR-SB, and ADAS-Cog) will be analyzed in subjects with EAD as well as separately within subjects with MCI and mild AD dementia. (revised per Amendment 10)

In addition, as sensitivity analysis, MMRM analysis will be performed for the following treatment comparisons: (revised per Amendment 10)

- Combining 2 high doses (10 mg biweekly + 10 mg monthly), 2 middle doses (5 mg biweekly + 5 mg monthly), and the 2.5 mg biweekly dose, resulting in 3 treatment comparisons with placebo (for dose response) (revised per Amendment 10)
- ED₉₀ dose of BAN2401 versus placebo, where the ED₉₀ dose of BAN2401 will be established by Bayesian analysis at 18 months as described in the next paragraph (revised per Amendment 10)
- By treatment regimen (10 mg biweekly, 10 mg monthly, 5 mg biweekly, 5 mg monthly, 2.5 mg biweekly, placebo) (revised per Amendment 10)
- Combining the top 3 doses (10 mg biweekly, 10 mg monthly, and 5 mg biweekly) versus placebo (revised per Amendment 10)

Change from baseline in the ADCOMS at 18 months will be analyzed, as a sensitivity analysis to the conventional analysis, using the same Bayesian methodology as that for analysis of change from baseline in the ADCOMS at 12 months, but using the full 18 months of efficacy data with the model projecting to 18 months of treatment. The Bayesian analysis of change from baseline in the ADCOMS at 18 months is positive if the analysis results in an ED₉₀ dose with at least an 80% probability of being better than the placebo by the CSD. The ED₉₀ dose will be identified based on change from baseline in the ADCOMS at the 18 month Bayesian analysis and will be used to compare ED₉₀ dose of BAN2401 and placebo in the above sensitivity analyses for all key secondary endpoint analyses. (revised per Amendments 09 and 10)

ANALYSIS FOR OTHER SECONDARY EFFICACY ENDPOINTS

The same analysis described above for key secondary endpoints will be performed for other secondary endpoints. (revised per Amendment 10)

EXPLORATORY EFFICACY ANALYSES

The same analysis described above for key secondary endpoints will be performed for exploratory endpoints. (revised per Amendment 10)

The effect of baseline brain amyloid pathophysiology as measured by amyloid PET on change from baseline in clinical status at 12 and 18 months of treatment will be explored using correlation analysis and evaluated using statistical models as appropriate. (revised per Amendment 10)

The relationship between change from baseline in clinical status and change from baseline in brain amyloid pathophysiology at 12 and 18 months of treatment as measured by amyloid PET will be explored by correlation analysis. (revised per Amendment 10)

Change in ADCOMS and its components, ADAS-Cog, CDR-SB, and MMSE across all clinical assessment time points between BAN2401 and placebo in Japanese subjects will be evaluated using the descriptive statistics within Japanese subjects as well as with the overall population. (revised per Amendments 07 and 10)

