9.1.2.1 Treatment Period

Subjects will be randomized at the beginning of the Treatment Period, and will receive study drug by infusion at every visit except the last visit, except for those subjects participating in the Extension Phase, as indicated in the Schedule of Assessments/Procedures ([Table 8](#), and [Table 13](#) for the Extension Phase Part A). (revised per Amendment 08 and 19) Double-blinding to study treatments will be in effect throughout the Core Study. Doses will not be changed. (revised per

Amendment 08) If a given subject cannot tolerate a give dose regimen, the subject will be discontinued from the study and will undergo an Early Termination Visit. During the Treatment Period, a subject may develop acute medical conditions unrelated to the study drug which in the opinion of the PI, may make them unsuitable to receive the study drug for 1 or more dose administrations. In this situation, the investigator should exercise clinical judgment as to whether or not to withhold a dose. As a general principle, temporary suspension of dosing may be considered and resumed after the acute medical condition has improved.

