9.7 STATISTICAL METHODS

All statistical analyses will be performed by the sponsor or designee after the database is locked and released for unblinding. (revised per Amendment 07) At each IA of the primary endpoint, a snapshot of the data will be obtained and released for analysis. A copy of this snapshot will be archived. This process will also be followed for the safety data that will be used for analysis for the DSMB. Statistical analyses will be performed using SAS software or other validated statistical software as required. All statistical tests will be based on the 10% level of significance, except for the Bayesian methods on the primary endpoint (revised per Amendments 09 and 10). Details of the statistical analyses will be included in a separate statistical analysis plan (SAP).

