9.7.1.9 Determination of Sample Size

The sample size and design characteristics to test the hypothesis under the primary objective based on the primary endpoint, the Composite Clinical score at 12 months, were determined by means of simulations. Extensive trial simulations have shown that a total of 800 subjects will be sufficient to demonstrate that the most likely ED₉₀ dose achieves a CSD from placebo with a probability of at least 95% in the IA and greater than 80% in the final analysis if the trial does not stop for early success. There is at least 80% probability of study success for the dose response scenarios where the treatment was considered to have clinically meaningful treatment effect. Simulations have also shown that if there is no efficacy at all for any dose, then the probability of falsely claiming superiority to placebo is no more than 10.0% assuming a 20% dropout rate.

For each of the 6 treatment groups (5 active dose regimens and placebo) the final number of subjects per group will differ depending on the observed interim treatment responses. The simulation plan will be described in the appendix section of the Statistical Analysis Plan, which will present further details.

vMRI

The null hypothesis is that there is no difference between active dose and placebo. There are 5 null hypotheses corresponding to 5 active dose regimens. The alternative hypothesis is that at least 1 null hypothesis is false (1-sided). The null hypotheses will be tested using Dunnett method with 1-sided alpha of 0.05. The statistical power was estimated through simulation for a moderate dose-response assumption that the percent reduction in change from baseline of total hippocampal volume compared to placebo would be 15%, 20%, 25%, 15%, and 20% corresponding to the 5 dose regimens (2.5, 5, and 10 mg/kg biweekly, 5 and 10 mg/kg 4-week interval), respectively. The estimated power for actual planned study sample size is 0.764 at 12 months and 0.694 at 18 months, assuming an attrition rate of 20% at 12 months and an exponential dropout model. Under a stronger dose-response assumption (ie, the percent reduction in change from baseline of total hippocampal volume compared to placebo is twice as much as that in the moderate dose-response assumption), the estimated power is at least 99% at both 12 and 18 months.

AMYLOID PET (IMAGING SUBGROUP)

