The study will be monitored for early success and early futility (see [definitions in Study Definitions](#)). The first IA will be conducted when 196 subjects are randomized, again when 250 subjects are randomized and again after each additional 50 subjects until 800 subjects are randomized. Sites in Japan will randomize at least 40 Japanese subjects, even if early success is declared or the study achieves 800 subjects randomized. In these circumstances, subjects in Japan will be allocated treatment according to the latest (or last) allocation schedule. If the study reaches its maximum of 800 randomized subjects, additional IA will be conducted every 3 months until all subjects complete 12 months of treatment. Only those subjects who were randomized before the target of 800 was met will contribute to these additional IA, except for the full 12 and 18 month Bayesian analyses. The study will be monitored for futility at each IA and for success starting at the 350 subject IA, until the full 12 months of treatment have been completed. (revised per Amendment 09) Each IA will be conducted on data for the derived Clinical Composite Score. If the efficacy or futility boundary is reached, the IMC will communicate directly with the DSMB members. (revised per Amendment 07)

The study may be stopped for safety reasons at any time.

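### The key secondary endpoints may be tested at 10% at the time of success and again at 18 months, and the protocol neither divides the 10% nor calls the first analysis descriptive

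*Protocol*

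**What the plan says.** Section 9.7.1.6, under the analysis of key secondary efficacy endpoints, sets two analysis times: "Conventional analysis will be performed using all available data at the time of success (if applicable), and at 18 months of treatment", the second of them whether or not success was declared. The synopsis repeats this. The comparison is also fixed: "An MMRM will be used to compare the combined 10 mg dose group (including biweekly and monthly regimens) with placebo for the key secondary endpoints".

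Section 9.7 and the synopsis set a single level: "All statistical tests will be based on the 10% level of significance, except for the Bayesian methods on the primary endpoint". Whether the 10% is one-sided or two-sided is not stated.

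The date of the first analysis depends on the Bayesian monitoring in section 9.7.2: "The study will be monitored for futility at each IA and for success starting at the 350 subject IA". Under section 9.7.1.6, success may also be declared at the full 12-month Bayesian analysis. Section 9.7.1.1 defines every key secondary endpoint as a change from baseline at 18 months.

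**The concern.** Read together, these sections allow the same endpoint to be tested twice on overlapping data, each time at the full 10%. Nothing says that a significant result at the time of success is only supportive. An endpoint on which the drug has no effect would then have two chances to be called significant, and the two results could differ.

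The only error rate that the protocol quantifies is in section 9.7.1.9: "the probability of falsely claiming superiority to placebo is no more than 10.0% assuming a 20% dropout rate". That figure belongs to the simulated primary Bayesian rule and does not cover the MMRM tests of the key secondary endpoints.

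**Working it through.** The 10% is a chosen level, and the protocol states no overall error rate across the two analyses, so there is no figure to reproduce. The check asks what error rate the stated rules imply.

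Inputs:
- Level at each analysis: 10% (section 9.7), taken as two-sided, so the critical value is 1.645.
- Probability p that the first analysis takes place: 0.80 if the drug works, from section 9.7.1.9 ("There is at least 80% probability of study success for the dose response scenarios" in which the effect is clinically meaningful). If no dose works, the same section gives at most 0.10.
- Information fraction t at the first analysis: **not in the protocol**. It is assumed to lie between 0.25 and 0.90.

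Step 1, both analyses take place. For one null endpoint, (Z1, Z2) is bivariate normal with correlation √t, and

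E2(t) = 1 − P(|Z1| < 1.645 and |Z2| < 1.645).

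Step 2, the first analysis takes place only on success, and success is independent of the endpoint:

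E(t) = 0.10 + p × (E2(t) − 0.10).

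At t = 0.25, E2 = 0.1755. With p = 0.80 this gives 0.10 + 0.80 × 0.0755 = 0.160. With p = 0.10 it gives 0.10 + 0.10 × 0.0755 = 0.108.

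| t | both analyses occur | p = 0.80 | p = 0.10 |
|---|---|---|---|
| 0.25 | 0.176 | 0.160 | 0.108 |
| 0.50 | 0.160 | 0.148 | 0.106 |
| 0.75 | 0.142 | 0.133 | 0.104 |
| 0.90 | 0.126 | 0.121 | 0.103 |

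Step 3, sensitivity of these figures:
- If the 10% is one-sided and both analyses occur, the error is 0.168 (t = 0.25) down to 0.122 (t = 0.90).
- The correlation √t supposes that both analyses estimate the same contrast. At an early trigger there may be little 18-month data, and postbaseline PET and CSF are collected only at 12 and 18 months. If the two tests were independent, the error would be 1 − 0.9² = 0.19.
- The 0.80 is the probability of success at any time, including the full 12-month analysis, when t should be larger. That favours the lower part of the p = 0.80 column.
- For an endpoint tied to ADCOMS when ADCOMS itself is null, suppose that the trigger is the endpoint's own first statistic exceeding 1.28 (an assumption). Then E = 0.10 + P(Z1 > 1.645 and |Z2| < 1.645), which is 0.138, 0.130, 0.121 and 0.113 at the four values of t.

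Step 4, after the fix. With the 18-month analysis as the only test, the error for one endpoint is 0.10 by construction. Keeping two tests with equal nominal levels would need about 0.055, 0.061, 0.069 or 0.079 at each analysis for t = 0.25, 0.50, 0.75 or 0.90.

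**The case against.** The strongest reply is that the protocol already points to the 18-month result. The endpoints are defined at 18 months, the 18-month analysis is unconditional, and the earlier one is conditional. No sentence lets significance at the earlier analysis count as a claim. This is a Phase 2 dose-finding study whose success rests only on the Bayesian ADCOMS rule, with no family-wise control promised for the key secondary endpoints. Details are left to the SAP, which was not at hand here.

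Much of this stands. The text does not set up two decision points of equal rank, and the missing piece is small. But the level in section 9.7 covers all conventional tests, both analyses fall under it, and neither is called descriptive. An SAP that treated the first analysis differently would have to depart from that wording.

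A reader might infer two stronger points that the protocol does not support:
- **That 0.12 to 0.16 applies to every key secondary endpoint.** It needs an endpoint that is null and independent of ADCOMS while ADCOMS responds. Table 10 shows that ADCOMS contains all six CDR items and four ADAS-Cog items, so this does not fit CDR-SB, ADAS-Cog or ADCOMS at 18 months.
- **That the analysis at the time of success breaks the blind.** Section 9.1.2.1 says "Double-blinding to study treatments will be in effect throughout the Core Study". Section 9.4.6 keeps sites and sponsor blinded, section 9.7 places the statistical analyses after lock and release for unblinding, and section 9.7.2 routes interim results through an independent group to the monitoring committee. Nothing releases these results to sites or raters.

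**Conclusion.** The point holds as a gap in what the protocol fixes: two scheduled analyses of the same endpoints, one undivided 10% level, and no statement that the first is descriptive. When both analyses take place, the error for one null endpoint is about 0.13 to 0.18 in place of 0.10. Weighted by an 80% chance of success, it is about 0.12 to 0.16 for a null endpoint independent of ADCOMS (PET, CSF or vMRI). When success is rare and unrelated to the endpoint, it is under 0.11. All of these figures rest on assumed information fractions and a two-sided reading of the 10%.

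The practical reach is limited. Sections 7.1.2.3 and 7.2.1.2 say that the Core Study was complete at Amendment 11. Table 2 shows 245 + 609 = 854 subjects in the Safety Analysis Set, so early success evidently did not cut randomization short. The protocol does not say whether an analysis at the time of success was ever triggered. What remains at stake is which p-value for a key secondary endpoint may be read as a test.

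**What to change.** In section 9.7.1.6 and the synopsis, state that the 18-month analysis is the sole inferential test of the key secondary endpoints at the 10% level. State also that any analysis at the time of success is descriptive, giving estimates and intervals without a claim of significance. This matches the endpoint definitions in section 9.7.1.1.

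The cost is one sentence in each place and the loss of an early formal claim on these endpoints. The 18-month test keeps its full 10% level, so it loses no power. With the Core Study complete, the change affects how the results are read and reported, and not how the trial is run.
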